7.2 Study Rationale

This first-in-human study is an open-label, multicenter, Phase 1, dose-finding study that will be conducted in 2 parts: a Dose Escalation phase (Part 1) and a Dose Expansion phase (Part 2). The primary objectives are to determine the MTD and/or the recommended Phase 2 dose (RP2D) of H3B-6527 and to assess the safety and tolerability of H3B-6527 as a single agent in subjects with advanced HCC.

H3B-6527 will be supplied as 50-, 100-, and 200-mg capsules and will be administered orally as a single-agent dose in 21-day cycles without a break; this is supported by nonclinical data showing tumor growth inhibition and regressions in human HCC xenograft models grown in nude mice. In addition, nonclinical safety evaluations with once daily (QD) dosing in mice and dogs have shown evidence of on-target pharmacology (eg, changes in circulating bile acid). The starting dose of 300 mg (first-in-human dose) is the human equivalent dose (HED) of 1/6th the highest non-severely toxic dose (HNSTD) in dog. The maximum single dose proposed in the current study is 2000 mg. It is also limited by the maximum number of capsules required to reach this dose.

The Dose Escalation Phase will follow a standard 3+3 cohort design. The dose will be escalated in successive cohorts based on a modified Fibonacci schema. The RP2D will be selected based on an integrated evaluation of available safety, tolerability, efficacy, pharmacokinetic (PK), and pharmacodynamic data for all dose levels on the defined schedule. The following considerations will help guide selection.

1. The RP2D must have <2/6 subjects experiencing a DLT at that dose (<33% DLT rate).
2. The overall safety profile, including AEs assessed as related to study drug treatment but not considered dose-limiting, as well as the nature, type, timing, and frequency of toxicities.
3. Tumor response(s).
4. Demonstration of proof of principle with respect to in vivo biologic activity. Mouse studies have shown an approximate 100-fold increase in cytochrome P450 (CYP) 7A1 tumor levels at efficacious doses. The proof of principle for H3B-6527 could be a robust increase in CYP7A1 tumor expression in humans.

Safety, tumor response, PK, and pharmacodynamic assessments will be performed on all subjects.

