9.1.1 Study Parts

9.1.1.1 Dose Escalation (Part 1)

The objective of Part 1, the Dose Escalation phase, is to determine the MTD/RP2D of H3B-6527 in subjects with advanced HCC. The selection of the RP2D will be based on an integrated evaluation of safety, tolerability, and clinical benefit, including PK and pharmacodynamic data. The total number of subjects to be enrolled will depend on the observed safety profile, which will determine the number of subjects per dose cohort, as well as the number of dose escalations required to achieve the MTD and/or RP2D of H3B-6527. Assuming 5 dose levels will be studied for the QD dose schedule and 3 dose levels for the BID dose schedule and a maximum of 6 subjects will be enrolled per dose level, approximately 30 to 48 subjects may be accrued during dose escalation. Subjects enrolled into Part 1, Dose Escalation phase, are not required to be FGF19-positive.

The criteria to evaluate at the BID dose schedule will be based on an integrated evaluation of safety, tolerability, clinical benefit, PK, and pharmacodynamic data, for all QD dose levels tested. In this case, a new cohort of 3 subjects will be enrolled and treated with a BID dose. The initial total daily dose given BID will be equal to a total daily dose that has been well tolerated as a QD dose (DLT rate <33% in a cohort of at least 3 subjects). If BID dosing of H3B-6527 is well tolerated in this initial cohort, then dose escalation may continue with BID dosing, following the same dose escalation rules applied to QD dosing. Additional cohorts of subjects may be enrolled to evaluate a less frequent dosing schedule (eg, daily for 2 consecutive weeks every 3 weeks [dosing on Days 1-14 of a 21-day cycle]).

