Once a subject has completed C3 at the initially assigned dose schedule and dose level (QD or BID), intrapatient dose escalation will be allowed. Only subjects who have not progressed on treatment and did not have a dose reduction or interruption because of a drug-related AE, will be permitted to escalate to the highest dose level that has completed DLT assessment within that dose schedule and has been shown to be safe (no DLT in the first 3 subjects or no more than 1 DLT in 6 subjects). Subjects on the intrapatient dose escalation will not be included in the DLT analysis at the higher dose level. The investigator and the medical monitor must agree that dose escalation is appropriate for the subject prior to escalating their H3B-6527 dose level.

The starting dose of 300 mg QD (first-in-human dose) is the HED of 1/6th the HNSTD in dog. Dose escalation will follow a modified Fibonacci design such that the magnitude of the escalation will decrease as the dose level nears the HED of the HNSTD in dogs (HED \approx 2000 mg).

Table 1 Dose Cohorts in H3B-6527 Dose-Escalation

Dose Level	Initial No. of Subjects	H3B-6527 Total Daily Dose
-1	3	150 mg
1 ^a	3	300 mg
2	3	600 mg
3	3	1000 mg
4	3	1400 mg
5	3	2000 mg

These total daily dose levels may be evaluated in QD or BID dose schedules, including intermediate dose levels, and in expansion of an existing dose level of up to 12 evaluable subjects following discussions between the Sponsor and the investigators, if supported by evolving safety, tolerability, PK, and pharmacodynamic data.

BID = twice daily, PK = pharmacokinetic, QD = once daily.

a: Planned starting dose level in QD schedule.

Refer to [Section 9.4.4.1](#) for details regarding the dose-escalation procedure.

The MTD is defined as the highest dose at which no more than 1 of 6 subjects experiences a DLT in the dose cohort. (Note that at least 6 subjects must be treated at the dose level potentially considered to be the MTD before that dose level can be considered the MTD). Therefore, if ≥ 2 subjects within a cohort experience a DLT and the previous dose level did not enroll 6 subjects, enrollment will move down to the previous dose level and continue until 6 subjects are enrolled, and the same guidelines for determining the MTD will be followed.

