The RP2D may not exceed the MTD and will be agreed upon by the SRC, based on an integrated evaluation of safety, tolerability, clinical benefit, PK, and pharmacodynamic data, for all dose levels tested. Clinically significant toxicities (eg, chronic Grade 2 toxicities) or AEs that meet the definition of dose limiting but occurring after C1 (dose-modifying events,

DME) may be considered when determining the RP2D. Once the MTD/RP2D is reached, at least 6 HCC subjects must be enrolled at the RP2D (regardless of the total number of subjects enrolled at that dose level) to proceed with dose expansion.

To be evaluable for a DLT, subjects must have completed safety assessments through predose on C2 Day 1 and must have received at least 17 of 21 (approximately 80%) study days within C1, unless due to a DLT. Subjects who discontinue from the study for reasons other than DLT before completing C1 are to be replaced. Subjects who experience toxicities meeting DLT criteria during C1 will be discontinued from treatment. In rare cases, an exemption to study discontinuation for a DLT in 1st cycle may be considered after discussion between the treating physician, Sponsor and study medical monitor. Subjects who experience toxicities meeting DLT criteria may, at the discretion of the investigator and after discussion with the Sponsor, be allowed to continue study drug at a reduced dose if this is judged to be in the best clinical interest of the subject. The Sponsor will communicate information about DLTs or safety concerns rapidly to all sites as per the separate Dose Escalation Plan, which also details the format and timelines of the Dose Escalation review meetings, and the communication of dose level decisions to all sites.

9.1.1.1.1 **DEFINITION OF DOSE-LIMITING TOXICITIES OR DOSE-MODIFYING EVENTS**

DLTs are defined as any of the toxicities listed in Table 2 occurring during C1 Phase 1 only and judged by the investigator as related to study drug (ie, assessed as unrelated to disease, intercurrent illness, or concomitant medications). Any event that occurs in C2 or beyond (including any cycle in Phase 2) will be considered a DME.

Table 2 Definition of Dose-Limiting Toxicity (Cycle 1 Phase 1 Only) or Dose-Modifying Event (Cycle 2 or Beyond and Any Cycle in Phase 2)

TOXICITY	CRITERIA

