9.4.4.1 Dose Escalation Scheme (Part 1)

The starting dose of H3B-6527 is 300 mg QD.

H3B-6527 doses will be escalated sequentially after the SRC, with appropriate representation from the Sponsor and participating investigators, reviews safety data collected during C1 from the subject(s) enrolled at the current dose level.

Subjects who do not receive study drug for at least 17 of 21 days (approximately 80%; not necessarily consecutively) during the first cycle for reasons not considered to be a DLT by both the investigators and the Sponsor will be replaced. The subjects who are replaced will not be considered evaluable for DLT assessments.

Based on the interim evaluation of the safety and tolerability data of the previous dose level, the Sponsor may decide to initiate accrual at an intermediate dose level. The SRC may be convened earlier at the discretion of the Sponsor if important safety issues arise requiring the attention of the committee.

Up to 3 subjects initially are to be enrolled. After 3 subjects complete C1 and have safety evaluations performed through C2 Day 1, and:

- None of these 3 subjects experience a DLT (see [Section 9.1.1.1.1](#)), then enrollment of the next cohort may commence with approval from the SRC.
- 1 of 3 subjects within a cohort experiences a DLT (see [Section 9.1.1.1.1](#)), then up to 3 additional subjects are to be enrolled sequentially at that dose level. If none of the

additional 3 subjects has a DLT (ie, 1 of 6 subjects has a DLT), then enrollment at the next scheduled dose may commence with approval from the SRC.

- If ≥ 2 subjects within a cohort experience a DLT (see [Section 9.1.1.1.1](#)), then the DLT dose level will have been reached and the previous lower dose level will be considered the MTD. Note that at least 6 subjects must be treated at the dose level potentially considered to be the MTD before that dose level can definitely be considered the MTD. Therefore, if ≥ 2 subjects within a cohort experience a DLT and the previous dose level did not enroll 6 subjects, enrollment will move down to the previous dose level and continue until 6 subjects are enrolled, and the same guidelines for determining the MTD will be followed.
 - Once the MTD or RP2D is established, additional subjects will be treated in the Expansion phase of the study (Part 2), which is designed to better characterize the safety, tolerability and preliminary antitumor activity of the study drug when provided at the RP2D and schedule.

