9.7.1.8 Safety Analyses

Evaluation of safety will be performed on the Safety Analysis Set except for the determination of the MTD during the dose escalation. The determination of the MTD will be based on all DLT-evaluable subjects enrolled in the Dose Escalation part.

Subjects who do not receive study drug for at least 17 of 21 days (approximately 80%; not necessarily consecutively) during the first cycle for reasons not considered to be a DLT by both the investigators and the Sponsor will be replaced. The subjects who are replaced will not be considered evaluable for DLT assessments.

Safety data to be evaluated include AEs, clinical laboratory results, vital signs, ECGs, and the results of ophthalmic examinations.

Safety parameters will be summarized using descriptive statistics (mean, standard deviation, median, Q1, Q3, and range for continuous variables; numbers and percentages for categorical measures).

The effects of H3B-6527 on cardiovascular repolarization will be evaluated via 12-lead continuous Holter/ECG monitoring on C1 Day 1 and on Day 8 in the Dose Escalation phase

of the study only. Individual ECGs will be extracted from the Holter recordings at specified time points per ECG manual and will be evaluated by a central laboratory. QT intervals will be measured from Lead II and will be corrected for QTcF correction factors. The primary QTc parameter will be QTcF; secondary parameters (QTcB, QT, QRS, QTcB, PR, and heart rate) and waveforms (T waves) will be evaluated.

9.7.1.8.1 **EXTENT OF EXPOSURE**

Descriptive statistics for subjects treated, including the duration of treatment, the number of cycles received, and the number of subjects requiring dose changes, will be presented. A by-subject listing of the date of study drug administration and the dose administered will be presented.

9.7.1.8.2 **ADVERSE EVENTS**

The AE verbatim descriptions (investigator terms from the CRF) will be classified into standardized medical terminology using the Medical Dictionary for Regulatory Activities (MedDRA). AEs will be coded to the MedDRA (Version 18.0 or higher) lower level term closest to the verbatim term. The linked MedDRA PT and primary system organ class (SOC) are also captured in the database.

A treatment-emergent adverse event (TEAE) is defined as an AE that emerges during treatment, having been absent at pretreatment (Baseline) or

- Reemerges during treatment, having been present at pretreatment (Baseline) but stopped before treatment, or

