### 3.2.2 Dose Escalation (Part 1)

The objective of the Dose Escalation phase is to determine the MTD and/or RP2D of H3B-6527 in subjects with advanced HCC. Intrahepatic cholangiocarcinoma (ICC) subjects were also enrolled from protocol Amendment 5 to Amendment 7.

For dose-escalation purposes, toxicities assigned as DLTs during the first cycle will be assessed. After 3-6 subjects in a cohort have completed Cycle 1 (C1), all available safety data will be reviewed by the Safety Review Committee (SRC) consisting of Sponsor personnel and investigators and the decision to proceed to the next dose cohort will be made jointly. Toxicities will be graded using the National Cancer Institute (NCI) Common Terminology Criteria for Adverse Events (CTCAE) version 4.03.

Once a subject has completed C3 at the initially assigned dose schedule and dose level (QD or BID), intrapatient dose escalation will be allowed.

H3B-6527 will be tested in sequential escalating dose cohorts (n=3 to 6) at the dose levels listed in the Table 1.

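### The plan lets a dose level hold 7 to 12 DLT-evaluable subjects, but its DLT decision rules agree only up to 6

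*Protocol*

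**What the plan says.** **MTD by count.** Protocol 9.1.1.1: "The MTD is defined as the highest dose at which no more than 1 of 6 subjects experiences a DLT in the dose cohort". The note that follows makes 6 a minimum, not a maximum. Under Protocol 9.4.4.1, once two or more subjects in a cohort have a DLT, "then the DLT dose level will have been reached and the previous lower dose level will be considered the MTD". That bullet gives no denominator. The Synopsis, the heading of Protocol Table 3 and SAP 3.2.2 tie the same rule to cohorts of 3 to 6.

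**RP2D by count, with a rate in brackets.** Protocol 7.2: "The RP2D must have <2/6 subjects experiencing a DLT at that dose (<33% DLT rate". Protocol 9.1.1.1 also says that the RP2D may not exceed the MTD.

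**BID start by rate.** Protocol 9.1.1.1 asks for a QD total daily dose that was "well tolerated as a QD dose (DLT rate <33% in a cohort of at least 3 subjects". The Synopsis (twice), Protocol 9.1, Protocol 9.4.4.1 and SAP 3.2.1 give the same rate but limit it to 3 to 6 subjects.

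**More than 6 at a level.** The note under Protocol Table 1 provides for dose levels to be evaluated "in expansion of an existing dose level of up to 12 evaluable subjects", and SAP Table 1 repeats this. Before expansion, "at least 6 HCC subjects must be enrolled at the RP2D (regardless of the total number of subjects" at that level. The SAP records that ICC "subjects were also enrolled from protocol Amendment 5 to Amendment 7", and the DLT Analysis Set in SAP 5.2.1 is not limited to HCC. Protocol 9.7.1.8: "The determination of the MTD will be based on all DLT-evaluable subjects enrolled in the Dose Escalation part".

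**The concern.** The plan treats fewer than two DLTs and a DLT rate below 33% as the same test. They are the same only while the cohort is small. From 7 subjects on, two DLTs fall below 33%, so the wording in one section can clear a level that the wording in another puts above the MTD.

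Determining the MTD and/or RP2D is a primary objective. SRC judgement cannot fully bridge the gap, because the RP2D is capped by an MTD whose rule is unclear at these sizes. A committee looking at, say, 2 DLTs in 9 evaluable subjects would have to choose a reading after seeing the data.

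**Working it through.** **Inputs.** Rate test: d/n < 33% (Protocol 7.2 and 9.1.1.1). Count test: d ≤ 1 (Protocol 9.4.4.1). Largest permitted n: 12 (notes under Protocol Table 1 and SAP Table 1). The documents give no DLT rate, so the true rates p below are assumptions.

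**1. The plan's own equivalence.** At n = 6, 1/6 = 16.7% passes both tests and 2/6 = 33.3% fails both, so the equation in Protocol 7.2 is right there. It also holds at n = 4 (1/4 = 25%, 2/4 = 50%) and n = 5 (1/5 = 20%, 2/5 = 40%). At n = 3, 1/3 = 33.3% fails the rate test, while the count rule only says to expand to 6, so there is no conflicting final verdict.

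**2. The same comparison above 6.**

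| n | Largest d with d/n < 33% | Largest d under the count bullet | Outcomes where they differ |
|---|---|---|---|
| 7 | 2 | 1 | 2/7 = 28.6% |
| 8 | 2 | 1 | 2/8 = 25.0% |
| 9 | 2 | 1 | 2/9 = 22.2% |
| 10 | 3 | 1 | 2/10 = 20.0%, 3/10 = 30.0% |
| 11 | 3 | 1 | 2/11 = 18.2%, 3/11 = 27.3% |
| 12 | 3 | 1 | 2/12 = 16.7%, 3/12 = 25.0% |

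That makes nine outcomes. Elsewhere the tests agree: 0 or 1 DLT passes both; 3 or more at n = 7 to 9 (3/9 = 33.3%) and 4 or more at n = 10 to 12 (4/12 = 33.3%) fail both.

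**3. The count bullet read at every size.** It rejects 2/12, which is the same 16.7% as the accepted 1/6. With q = 1 − p, P(at most 1 DLT) = q^n + n·p·q^(n−1). At p = 0.10:

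- n = 6: 0.531 + 0.354 = 0.886
- n = 12: 0.282 + 0.377 = 0.659
- Rate test at n = 12 (at most 3 DLTs): 0.974

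So adding subjects to a tolerable level makes its rejection more likely under the count reading.

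**4. How often the disputed zone is reached.** Take a level cleared at no more than 1 of 6, with a0 = q^6 and a1 = 6·p·q^5.

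- Filled to 12, Y ~ Bin(6, p): P(2 or 3 DLTs in total) = [a0·P(2≤Y≤3) + a1·P(1≤Y≤2)] / (a0 + a1). At p = 0.10 this is (0.531 × 0.113 + 0.354 × 0.453) / 0.886 = 0.249.
- Filled to 9, Y ~ Bin(3, p): P(2 DLTs in total) = [a0·P(Y=2) + a1·P(Y=1)] / (a0 + a1). At p = 0.10 this is (0.531 × 0.027 + 0.354 × 0.243) / 0.886 = 0.113.

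| True DLT rate (assumed) | Filled to 12 | Filled to 9 |
|---|---|---|
| 10% | 0.249 | 0.113 |
| 15% | 0.402 | 0.195 |
| 20% | 0.514 | 0.269 |
| 25% | 0.578 | 0.328 |

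**5. What each possible rule would accept at a true rate of 1/3.** Entries are P(D ≤ c), D ~ Bin(n, 1/3), where c is the rule's maximum count.

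| n | Count rule (1 throughout) | Below 33% (2 in 7–9, 3 in 10–12) | Stricter table (1 in 6–8, 2 in 9–11, 3 in 12) |
|---|---|---|---|
| 6 | 0.351 | 0.351 | 0.351 |
| 7 | 0.263 | 0.571 | 0.263 |
| 8 | 0.195 | 0.468 | 0.195 |
| 9 | 0.143 | 0.377 | 0.377 |
| 10 | 0.104 | 0.559 | 0.299 |
| 11 | 0.075 | 0.473 | 0.234 |
| 12 | 0.054 | 0.393 | 0.393 |

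**The case against.** The best defence is that the count rule was written for 3 to 6 subjects. The Synopsis, Protocol Table 3 and SAP 3.2.2 say so, and the bullet just before the one in Protocol 9.4.4.1 builds a cohort as 3 plus up to 3. For the BID start, only the 9.1.1.1 sentence lacks the upper limit of 6. Five parallel statements have it, and at 3 to 6 subjects the rules give no opposite final verdict. Sample size planning also assumes at most 6 per level. On this reading there is no contradiction beyond one loose sentence.

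Much of that stands, but it moves the fault rather than removing it. If the count rule stops at 6, nothing says how to judge the 7 to 12 evaluable subjects that both documents allow, although Protocol 9.7.1.8 and SAP 5.6 base the MTD on all evaluable Part 1 subjects.

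A reader might infer that the rules conflict whenever a level exceeds 6. They do not; only the nine listed outcomes are affected. A reader might also infer that a level rejected as above the MTD could still go into expansion on the 33% wording. The documents do not support that. In Protocol 7.2 the rate is a gloss on fewer than 2 of 6, within a list of considerations that guide selection, and Protocol 9.1.1.1 forbids an RP2D above the MTD. If the count rule applies above 6, it blocks that level.

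It is also fair to say that the frequencies are hypothetical. Expansion to 12 is discretionary, and ICC enrolment, one route to more than 6, has ended.

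**Conclusion.** The point holds as a minor gap in a decision rule. Up to 6 evaluable subjects the plan is coherent. At 7 to 12 it either gives conflicting answers at nine specific outcomes or, if the count rule is confined to 3 to 6, gives no MTD rule. No passage settles which.

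The enumeration needs no assumptions. The 25% to 58% (filled to 12) and 11% to 33% (filled to 9) depend on assumed true DLT rates of 10% to 25%, on the level having cleared at no more than 1 of 6, and on its being expanded. The documents do not say how often expansion will happen.

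**What to change.** 1. In Protocol 9.1.1.1, limit the BID-start rate to 3 to 6 subjects, as the Synopsis, Protocol 9.1 and 9.4.4.1 and SAP 3.2.1 already do. Add that the BID starting total daily dose may not exceed a QD level judged to be at or below the MTD.
2. In Protocol 9.1.1.1, Protocol 9.4.4.1 with Table 3, and the MTD definition in SAP 3.2.2, state one maximum DLT count for each number of evaluable subjects from 7 to 12. Use it for the MTD, the RP2D (Protocol 7.2) and the BID start.

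The cut-off is the sponsor's choice. The plan's own 33% would allow 2 in 7–9 and 3 in 10–12, but accepts a true one-in-three rate 38% to 57% of the time across those sizes. The stricter table (1 in 6–8, 2 in 9–11, 3 in 12) accepts it 20% to 39% of the time, against 35% for 1 of 6, and unevenly from one size to the next. Keeping a maximum of 1 at every size is also coherent if stated, at the price shown in step 3 of the working. Whichever is chosen, give its acceptance probability at a true rate of about 33%.

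The cost is wording in a few sections of both documents. It needs no extra visits and no change to any analysis set.

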Due to the potential for dropouts during the first cycle of treatment (eg, because of early disease progression), a cohort may initially be expanded to include up to 2 additional subjects. However, if these additional subjects are to be enrolled, they must start treatment ≤ 14 days after the third subject enrolled in the cohort was first dosed with H3B-6527. The decision to dose escalate may still be made after the third subject enrolled to the dose level in question has completed the first cycle of treatment. However, if under these circumstances the decision is made to enroll subjects to a higher dose level, and one of the additional subjects treated at the preceding dose level experiences a DLT in the first cycle of treatment, then further enrollment of subjects to the higher dose level will be suspended until it can be determined whether the preceding dose level exceeds the MTD. In the meantime, subjects enrolled to the higher dose level may continue treatment at that dose if they are tolerating it well, and if continuing treatment is considered appropriate for the toxicity in question.

For dose escalation purposes, toxicities assigned as DLTs during the first cycle will be assessed. After 3-6 subjects in a cohort have completed Cycle (C) 1, all available safety data will be reviewed by the SRC, consisting of Sponsor personnel and investigators, and the decision to proceed to the next dose cohort will be made jointly. If different dose schedules are explored, decisions regarding dose escalation will be made based on review of data from subjects enrolled in cohorts on the same schedule, however, safety data from alternate schedules may be considered by the SRC. Toxicities will be graded using the National Cancer Institute Common Terminology Criteria for Adverse Events ([CTCAE](#)), Version 4.03.

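### The intrapatient escalation test can pass a dose level on its first 3 subjects although the plan's own MTD rules reject that level on 6

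*Protocol*

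**What the plan says.** Protocol Section 9.1.1.1, repeated almost word for word in the synopsis under Dose Escalation (Part 1), covers subjects who have completed Cycle 3 without progression and without a drug-related dose reduction or interruption. Such a subject may "escalate to the highest dose level that has completed DLT assessment within that dose schedule and has been shown to be safe". The test for that last condition follows in parentheses: "no DLT in the first 3 subjects or no more than 1 DLT in 6 subjects". The investigator and the medical monitor must agree in each case.

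The same section sets the MTD rules. "The MTD is defined as the highest dose at which no more than 1 of 6 subjects experiences a DLT in the dose cohort", and "at least 6 subjects must be treated at the dose level potentially considered to be the MTD before that dose level" can take that status. If a cohort has 2 or more DLTs and the level below it has fewer than 6 subjects, "enrollment will move down to the previous dose level and continue until 6 subjects are enrolled". Section 9.4.4.1 repeats this and treats a cohort with 2 or more DLTs as having reached the dose-limiting level. Section 7.2 requires fewer than 2 of 6 subjects with a DLT (below 33%) at the RP2D.

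Two other routes add subjects after the first 3. Against early drop-out, "a cohort may initially be expanded to include up to 2 additional subjects". The text under Table 1 also allows dose levels to be studied "in expansion of an existing dose level of up to 12 evaluable subjects". If an extra subject has a DLT after the next level has opened, new enrollment to the higher level "will be suspended until it can be determined whether the preceding dose level exceeds the MTD".

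SAP Section 3.2.2 allows intrapatient escalation after Cycle 3 but states no safety test for the target level.

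**The concern.** The two limbs are joined by an or, and the first looks only at the first 3 subjects. For opening the next cohort that makes sense, because at that moment 3 subjects are all there are. An intrapatient request comes later: no earlier than three 21-day cycles (9 weeks) after the subject's first dose, by which time the target level may have been filled to 6. The text does not say that the first limb gives way to the fuller count.

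The same level can therefore satisfy the intrapatient test and fail the MTD definition. The fill-up is not an unusual route: it is what the protocol requires when the next level fails and the level below has fewer than 6 subjects. If the failed upper level meets neither limb, the filled-up level becomes the highest one that passes, and so the one the rule points to. The subjects concerned are those tolerating a lower dose without progression.

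**Working it through.** **Inputs.** Intrapatient test: 0 DLTs in the first 3, or at most 1 in 6 (Section 9.1.1.1 and synopsis). MTD rule: at most 1 in 6, with at least 6 treated (Section 9.1.1.1). Rejection: 2 or more DLTs in a cohort (Section 9.4.4.1). RP2D ceiling: fewer than 2 of 6, below 33% (Section 7.2). The documents give no true DLT rate, so *p* is an assumption, shown from 0.10 to 0.50; DLTs are taken as independent with the same *p* for all subjects at a level.

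**The plan's own figure.** 1/6 = 16.7% is below 33%; 2/6 = 33.3% is not. The stated ceiling reproduces and agrees with the MTD definition.

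**Where the rules disagree.** Let *a* be the DLTs in the first 3 subjects and *b* those in the next 3. There are 4 × 4 = 16 pairs (*a*, *b*). The intrapatient test passes if *a* = 0 or *a* + *b* ≤ 1; the MTD rule passes if *a* + *b* ≤ 1. They differ in exactly two pairs:

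- *a* = 0, *b* = 2: 2/6 (33.3%)
- *a* = 0, *b* = 3: 3/6 (50%)

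In both, the intrapatient test passes and the MTD rule rejects.

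**How often.**

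- Clean start: P(0/3) = (1 − *p*)³
- At least 2 DLTs in the next 3: 3*p*²(1 − *p*) + *p*³
- Joint, if 6 are treated: the product of the two

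| Assumed *p* | P(0/3) | P(≥2 of next 3), given 0/3 and fill-up | Joint |
|---|---|---|---|
| 0.10 | 0.729 | 0.028 | 0.020 |
| 0.20 | 0.512 | 0.104 | 0.053 |
| 0.30 | 0.343 | 0.216 | 0.074 |
| 0.40 | 0.216 | 0.352 | 0.076 |
| 0.50 | 0.125 | 0.500 | 0.062 |

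At *p* = 0.30, for example: 3 × 0.09 × 0.7 + 0.027 = 0.216, and 0.343 × 0.216 = 0.074.

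**A worked path.** 600 mg gives 0/3. 1000 mg gives 2 DLTs in its first 3. 600 mg is filled to 6 and ends at 2/6. Its DLT assessment is now complete and the MTD rule rejects it. For a subject on 300 mg who has completed Cycle 3, 600 mg still meets the first limb.

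**Does other text close the gap?**

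- The statement in Section 9.1.1.1 that the MTD may not be exceeded is about the RP2D only.
- The synopsis statement that additional subjects go to a lower level after 2 or more DLTs does not address subjects already on study.
- The agreement of investigator and medical monitor carries no DLT criterion.

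**The case against.** The strongest reply is that the parenthesis simply restates the two passing outcomes of the 3+3 scheme in Table 3, by cohort size: no DLT where 3 were treated, at most 1 where 6 were treated. On that reading a 2/6 level fails and nothing conflicts. This may well be what was meant. It is not what is written: the first limb refers to the first 3 subjects, not to a level with only 3, and no sentence retires it.

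A second reply is that the level must also have completed DLT assessment. That can reasonably be read to exclude a level whose status is pending because an extra subject had a DLT, so the pending case is less certain. The hold there mentions new enrollment only, and the plan does not say which subjects' assessment must be complete. The condition does not help with a level that has finished at 2/6 or 3/6.

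Third, there are human safeguards. The investigator and medical monitor must agree, the Safety Review Committee reviews data from subjects continuing treatment (Section 9.4.4.1), and a separate Dose Escalation Plan, not among these documents, governs how dose-level decisions reach sites. These make such an escalation unlikely in practice, and the Dose Escalation Plan may already deal with it. They do not remove the contradiction from the protocol.

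**Conclusion.** The point stands as an internal contradiction, confined to a level with 0/3 that is filled to 6 and ends at 2/6 or 3/6. Given a clean first 3 and fill-up, the two rules disagree with probability 10%, 22% and 35% at assumed rates of 0.20, 0.30 and 0.40; jointly with the clean start, 5.3%, 7.4% and 7.6%. These figures rest on independence, on assumed rates and on 6 subjects being treated. The contradiction itself rests on the text alone.

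Three stronger readings are not supported:

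- A reader might take 5% to 8% as the chance that a subject is harmed. Harm would also need an eligible subject at a lower dose, a request, agreement from both the investigator and the medical monitor, and then toxicity.
- A reader might conclude that toxicity in escalated subjects goes unnoticed because they are left out of the DLT analysis at the higher level. That exclusion concerns the formal count, and DLTs are limited to Cycle 1 by definition. Ongoing safety data go to the Safety Review Committee, and later dose-modifying events may inform the RP2D.
- A reader might add the chance of a DLT in the 2 extra subjects after a clean first 3: 0.512 × 0.36 = 18.4% at *p* = 0.20 and 0.343 × 0.51 = 17.5% at 0.30. Most of this is a single DLT (0.512 × 0.32 = 0.164, or 89%; 0.343 × 0.42 = 0.144, or 82%), which the plan does not reject.

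**What to change.** Reconcile the parenthesis in Section 9.1.1.1 and in the synopsis with the MTD definition in the same section, the rejection rule in Section 9.4.4.1 and the RP2D ceiling in Section 7.2, so that one level cannot both pass the intrapatient test and be rejected. In the same edit, state how the intrapatient rule relates to the hold on enrollment after a DLT in an extra subject, and whose DLT assessment must be complete. Which rule applies, and its wording, are for the sponsor and the Safety Review Committee to decide.

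The cost is about one sentence in each of two places at the next amendment, and possibly a delay for a few escalation requests while a level is being filled.
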